## List of Abbreviations

ARDS	Acute Respiratory Distress Syndrome
APACHE II	Acute Physiologic Assessment and Chronic Health Evaluation II
ASR	Annual Safety Report
CA	Competent Authority
CAS-1R	Cognitive Attentional Syndrome Scale-1 (Revised)
CI	Chief Investigator
COVID-19	Coronavirus Disease 2019
CRF	Case Report Form
HADS	Hospital Anxiety and Depression Scale
HRQoL	Health-Related Quality of Life
ICU	Intensive Care Unit
ICM	Intensive Care Medicine
IES-6	Impact of Event Scale-6
IES-R	Impact of Events Scale-Revised
Main REC	Main Research Ethics Committee
NHS	National Health Service
NIHR	National Institute for Health Research
PI	Principle Investigator
PICS	Post-Intensive Care Syndrome
PTSD	Post Traumatic Stress Disorder
R&D	Research & Development
RD&I	Research, Development and Innovation
REC	Research Ethics Committee
REDCap	Research Electronic Data Capture
SAE	Serious Adverse Event
SARS	Severe Acute Respiratory Syndrome
SARS-CoV-2	Severe Acute Respiratory Syndrome Coronavirus 2
SOFA	Sequential Organ Failure Assessment
SOP	Standard Operating Procedure
TRIC	Trainee Research in Intensive Care

## 1. Study Summary

Title	The psychological impact of surviving an intensive care admission due to coronavirus disease 2019 (COVID-19) on patients in the United Kingdom
Protocol short title / Acronym	Psychological Impact of COVID-19 on Intensive Care Survivors / PIM-COVID
Protocol Version number and Date	Version: 1.6 8 April 2022
IRAS	282400
Is the study a Pilot?	No
Study Duration	24 months
Methodology / Study Design	Mixed methods: multicentre longitudinal observational study, longitudinal semi-structured interviews and observational structured survey.
Sponsor	Liverpool University Hospitals NHS Foundation Trust
Co-Chief Investigators	[name] [name]
Medical conditions under investigation	1) Anxiety, 2) depression and 3) trauma symptoms
Purpose of study	To assess the short- and long-term psychological impact on patients who have survived an admission to intensive care due to COVID-19, and identify possible predictors of anxiety, depression and trauma symptoms in this patient group.
Primary objective	To identify the proportion of patients surviving an admission to intensive care due to COVID-19 who experience anxiety, depression and/or trauma symptoms in the 6 months post-discharge, assessed using the Hospital Anxiety and Depression Scale (HADS) and the Impact of Event Scale-6 (IES-6), respectively.
Secondary objectives	
 
Identify demographic, clinical, physical and/or psychosocial predictors of depression, anxiety and/or trauma symptoms at 3-, 6- and 12-months post discharge from ICU.
 

	
 
2. Assess the feasibility of using a self-reported online questionnaire to assess anxiety, depression and/or trauma symptoms in patients following ICU admission.
 
3. Explore the experiences of critical care survivors following COVID-19 infection during their recovery phase, including perceptions about the care received and support available to them, using semi-structured interviews
 
4. Assess geographical differences in the availability and structure of follow-up services offered to patients with critical COVID-19 after hospital discharge.
 
5. Gain feedback from the study team members on their involvement in the study.
 

Main Inclusion and Exclusion Criteria	
Inclusion criteria:
 
 
1. Adult patients <math>\geq 18</math> years
 
2. Survived to intensive care / high dependency unit discharge following an admission of <math>\geq 24</math> hours
 
3. Diagnosed positive for COVID-19
 
 
Exclusion criteria:
 
 
1. Unable to complete questionnaires
 
2. Unable or unwilling to consent
 
3. Unable to speak, understand or communicate in English
 
4. Patients with diagnosed pre-existing cognitive impairment (at the time of ICU admission)
 
5. Patients with no fixed abode, at which postal questionnaire might be not received, and who have no access to a personal email address.
 

Randomisation	Not applicable
Statistical Methodology and Analysis	Trajectories of anxiety, depression, and trauma symptoms will be estimated using growth curve analysis. We will estimate and predict individual survivors' slope and intercept scores. We will then regress predictor variables onto intercept and slope scores for all outcomes to identify variables likely to determine trajectories of anxiety, depression and trauma symptoms. Feasibility will be assessed using descriptive analyses.

## 2. Introduction

Severe acute respiratory syndrome coronavirus-2 (SARS-CoV-2) was first reported in Wuhan, China in December 2019 (1). SARS-CoV-2 was later termed coronavirus disease 2019 (COVID-19) by the World Health Organisation (WHO). On March 12, 2020 a pandemic was declared, which continues to emerge globally (2). At the time of writing, COVID-19 infections number over one million and have been responsible for over 123,000 deaths worldwide (3).

COVID-19 is responsible for a spectrum of clinical presentations, ranging from asymptomatic or mild disease in the majority of patients, to pneumonia and acute respiratory distress syndrome (ARDS) in those more severely affected (1). Initial reports suggested 5% of 1099 patients in China with confirmed COVID-19 were admitted to an intensive care unit (ICU) (4). Meanwhile, 12% of positive cases required ICU admission in Lombardy, Italy, accounting for 16% of all hospitalised patients (5). Based on recent UK-wide data from 258 ICUs where at least one patient has had COVID-19, the ICU mortality rate amongst patients with confirmed COVID-19 is 41.1% (6).

In a 5 year longitudinal study of patients who developed ARDS not caused by COVID-19, prolonged symptoms of anxiety, depression and post-traumatic stress disorder (PTSD) were found to affect 23-38% of patients, with a median duration of symptoms of between 33 and 39 months (7). Not all patients admitted to ICU with COVID-19 will have ARDS, but admission to ICU is itself associated with a significant burden of post-ICU psychological sequelae. Symptoms of anxiety, depression and PTSD have been reported to affect up to 73% of survivors (8-10). Furthermore, symptoms of anxiety, depression and PTSD persist in 34% (8), 29% (9) and 34% (10) of ICU survivors respectively at 12-14 months following ICU admission.

The severe acute respiratory syndrome (SARS) pandemic in 2002-2003 was also caused by a coronavirus, but affected significantly fewer individuals despite having a higher case fatality rate (10.9% (11) vs 3.2% (4)). At the peak of the SARS outbreak, patients reported significantly higher stress levels than healthy controls (12), with similar symptoms reported up to 1 year later, with 64% of patients reporting symptoms suggesting psychiatric morbidity (13). Furthermore, amongst SARS survivors, females were more likely to have symptoms of anxiety, depression, stress and trauma, and were three times more likely than males to have psychiatric morbidity (13). Female gender was also found to be an independent risk factor for chronic PTSD up to 30 months after the SARS outbreak (14). These results contrast with pre-existing data for ICU survivors, in whom gender is not a significant risk factor for anxiety, depression or PTSD (8-10). Instead, recognised risk factors for emotional distress following ICU

admission include previous psychiatric morbidity, receipt of benzodiazepines in ICU and psychiatric symptoms during admission (8-10). Furthermore, psychological symptoms may be part of Post Intensive Care Syndrome, which also includes cognitive and physical impairments that are new or have worsened following ICU admission and persist on discharge from hospital (15, 16).

Whilst data emerges about the short-term impact of COVID-19 (17), the long-term implications to patients and healthcare systems remain unclear. With population-wide social distancing and societal lockdown enacted in many countries, the mental health of the general public is under strain(18). Data from previous pandemics suggests that pandemic-related factors such as quarantine may also have an impact on the psychological wellbeing of ICU survivors (19). It is plausible that this heightened anxiety primes patients, who subsequently require treatment in ICU for COVID-19, to develop psychological distress (17).

We anticipate that there will be a significant burden to healthcare systems as a result of psychological distress. Current national guidelines state that at-risk ICU survivors who have had an admission of more than 4 days should be invited to a follow up clinic 2-3 months after discharge from ICU (20). However, hospital and community based services to support ICU survivors in their recovery were limited before COVID-19, with some hospitals not even offering an ICU follow up clinic (21). The number of patients expected to require admission to ICU during COVID-19 is far beyond existing UK critical care capacity, and in the context of enhanced baseline societal anxiety, the potential volume of patients with post-ICU psychological distress could far exceed existing healthcare capacity overwhelming current services. In order to be able to expand services as necessary and support ICU survivors properly to help them regain their quality of life, and return to working and contributing to society, we must first identify how many, and to what extent patients are affected.

In this study, we aim to: 1. identify the proportion of COVID-19-positive critical care survivors who experience anxiety, depression and/or trauma symptoms up to 12 months after discharge from ICU, using validated tools; 2. identify predictors of post-ICU anxiety, depression and/or trauma in COVID-19 ICU survivors; 3. explore the experiences of critical care survivors following COVID-19 infection during their recovery phase, including perceptions about the care received and support available to them and 4. assess geographical differences in the availability and structure of follow-up services offered to critical COVID-19 survivors. This information may be used to inform healthcare systems about the psychological support required for survivors of this pandemic, and may inform healthcare planning for future pandemics.

### **3. Study Objectives, Design and Statistics**

#### **3.1 Study Aim**

To assess the short- and long-term psychological impact on patients who have survived an admission to intensive care due to COVID-19 in the United Kingdom, and identify possible predictors of anxiety, depression and trauma symptoms in this patient group.

#### **3.2 Study Objectives**

##### **Primary objective:**

To identify the proportion of patients who survive ICU admission following treatment for COVID-19 that experience anxiety, depression and/or trauma symptoms at 6 months, assessed using the Hospital Anxiety and Depression Scale (HADS) and the Impact of Event Scale-6 (IES-6), respectively.

##### **Exploratory objectives:**

1. Identify demographic, clinical, physical and/or psychosocial predictors of depression, anxiety and/or trauma symptoms at 3-, 6- and 12-months after ICU discharge in patients being treated for COVID-19 within the ICU.
2. Assess the feasibility of using a self-reported questionnaire to assess anxiety, depression and/or trauma symptoms in patients following ICU admission with COVID-19.
3. Explore the experiences of critical care survivors following COVID-19 infection during their recovery phase, including perceptions about the care received and support available to them, using semi-structured interviews.
4. Assess geographical differences in the availability and structure of follow-up services offered to patients with critical COVID-19 after hospital discharge.
5. Gain feedback from the study team members on their involvement in this trainee-led study.

### **3.3 Study Outcomes**

##### **Primary outcome:**

Prevalence and incidence of:

1. Anxiety
2. Depression
3. Trauma

Anxiety and depression will be assessed using the HADS. The HADS is a 14-item self-report measure in which participants rate the presence of symptoms of anxiety (7 items) and depression (7 items) over the

preceding week using a 4-point Likert scale, with options from 0 (absence) to 3 (extreme presence). Responses are summed to produce two subscale scores, ranging from 0-21, with higher scores indicative of higher anxiety and depression levels, respectively. The HADS is widely used to assess anxiety and depression in people with physical health difficulties and demonstrates good psychometric properties when used in an intensive care setting. Cut-off scores of  $\geq 8$  on anxiety and depression subscales of the HADS were used to define caseness (22, 23). A recent meta-analysis (24) showed the anxiety cut-off to predict structured interview diagnoses of either anxiety or depression with a sensitivity of 73% and specificity of 65%, and the depression cut-off to predict diagnosed depression with a sensitivity of 86% and specificity of 81%.

Trauma will be assessed using the IES-6. The IES-6 is a validated tool in survivors of ARDS for screening for post-traumatic stress disorder. It is an abbreviated version of the IES-R test and contains six questions (25). We have chosen the IES-6 over the IES-R because it is shorter, is validated in a very similar patient population, will provide similar information, and is likely to have a higher completion rate by patients because it is shorter. Furthermore, in collaboration with ICU steps it was felt that this was the best approach for this cohort of ICU survivors.

**Exploratory outcomes:**

1. Identify demographic, clinical, physical and/or psychosocial predictors of depression, anxiety and/or trauma symptoms at 3-, 6- and 12-months post discharge from ICU.

a. Demographic and clinical predictors.

(See Schedule of Study Procedure for specific data that will be collected.)

b. Physical predictors.

The EuroQol 5-dimension, 5-level questionnaire (EQ-5D-5L) is a five-domain, self-report measure assessing mobility, self-care, usual activities, pain/discomfort and anxiety/depression. Participants are asked to rate each question, indicating no problems, slight problems, moderate problems, severe problems or extreme problems. In addition, participants are invited to rate their health on a visual analogue scale from 0-100, where zero represent the worst health imaginable and 100 represents the best health imaginable. EQ-5D-5L is the recommended questionnaire to assess the HRQoL of critically ill patients (26). In this study, EQ-5D-5L will be used as a subjective assessment of the physical function of participants.

c. Psychosocial predictors (metacognitive beliefs and processes).

Metacognitive beliefs and processes will be assessed using the Cognitive Attentional Syndrome Scale-1 (Revised; CAS-1R (27)). The CAS-1R is a 10-item self-report measure assessing positive and negative metacognitive beliefs, frequency of worry/rumination and the use of a range of counterproductive coping strategies used in response to negative thoughts and feelings. Participants are asked to rate the degree to which they have engaged in a particular coping strategy or thought process during the previous week. Responses are scaled from 0%-100% and are summed to produce a total score. Higher scores indicate greater conviction in metacognitive beliefs and greater use of maladaptive coping strategies to manage distress. The CAS-1R has demonstrated good psychometric properties in physical health populations.

2. Assess the feasibility of using a self-reported online questionnaire to assess anxiety, depression and/or trauma symptoms in patients following ICU admission.

Outcomes:

- Recruitment number (total number of patients recruited per month)
- Recruitment rate (proportion of those deemed eligible recruited)
- Retention rate (proportion of participants who provide data at subsequent data capture points)
- Rate of missing key data
- Estimation of quantities needed for an accurate sample size calculation (e.g. HADS standard deviation)

3. Explore the experiences of critical care survivors following COVID-19 infection during their recovery phase, including perceptions about the care received and support available to them, using semi-structured interviews. The central study team will conduct semi-structured interviews in a representative sample of 40 patients. (See Schedule of Events for additional information.)
4. Assess geographical differences in the availability and structure of follow-up services offered to patients with critical COVID-19 after hospital discharge.
5. Explore the factors influencing the involvement of study team members in the study.

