### **3.5 Study Statistics**

This study is planned as a descriptive study in an effort to quantify the psychological impact on ICU survivors of COVID-19. It is anticipated that the study will report its findings using descriptive methods in the absence of a comparator group.

Trajectories of anxiety, depression, and trauma symptoms will be estimated using growth curve analysis. To improve power, we will use the full range of anxiety, depression and trauma symptom scores (not cut-off scores). Growth modelling is latent variable covariance modelling to estimate the intercept (value of the initial observation) and slope (the rate of change from this observation over time) of a time series of mean scores. We will estimate full sample single class models (eg, assuming homogeneity across the sample) for each outcome. Initial fixed parameters will be; error variance constrained to equality across observations, mean intercept and slope constrained to zero, intercept and slope constrained to equality, and intercept and slope covariance constrained to zero. Parameters will be systematically relaxed in that order until good fitting models ( $CFI > .95$ ,  $RMSEA < .05$ ) are identified with maximum fixed parameters. Linear and quadratic slope models will be tested; linear models being defined as slope parameters 0, 1, 4, and 12 and quadratic slopes as 0, 1, 8 and 24.

We will estimate and predict individual survivors' slope and intercept scores. Scores will be calculated using the regression method, setting intercepts for observed variables to 0 and imposing equality of variance. We will then regress predictor variables onto intercept and slope scores for all outcomes to identify variables likely to determine trajectories of anxiety, depression and trauma symptoms.

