#### **Psychological assessment via self-reported questionnaire:**

The following four self-report questionnaires will be administered at 3, 6 and 12 months following ICU discharge:

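### CAS-1R and EQ-5D-5L share the 3-month questionnaire with the symptom scores that start the growth curve, so their intercept links are concurrent and their slope links can be false

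*Combined protocol and SAP*

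**What the plan says.** Section 3.3 gives exploratory outcome 1 as: "Identify demographic, clinical, physical and/or psychosocial predictors of depression, anxiety and/or trauma symptoms at 3-, 6- and 12-months post discharge from ICU". CAS-1R is the psychosocial predictor and EQ-5D-5L the physical one.

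On timing, section 5.3 states: "The following four self-report questionnaires will be administered at 3, 6 and 12 months following ICU discharge". The four are HADS, IES-6, CAS-1R and EQ-5D-5L. The schedule lists no earlier value of any of them.

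On content, section 3.3 describes both HADS and CAS-1R as asking about the past week. It uses EQ-5D-5L as the subjective measure of physical function, and describes it as "assessing mobility, self-care, usual activities, pain/discomfort and anxiety/depression". Nothing says that the last of these domains is left out.

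On analysis, section 3.5 describes growth modelling as a way to "estimate the intercept (value of the initial observation) and slope (the rate of change from this observation over time". On this schedule the initial observation is month 3. For individual scores: "Scores will be calculated using the regression method, setting intercepts for observed variables to 0 and imposing equality of variance". Then: "We will then regress predictor variables onto intercept and slope scores for all outcomes to identify variables likely to determine trajectories". No predictor wave, lag or allowance for shared same-occasion variance is stated.

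**The concern.** For CAS-1R and EQ-5D-5L, the regression on the intercept relates two things reported on the same form. If 6- or 12-month values were used instead, the predictor would come after the observation that anchors the intercept. Neither shows what determines a trajectory.

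The slope regression has a less obvious fault. A bad week at month 3 can raise the predictor scale and the 3-month symptom score together. The symptom score then tends to fall back, so the scale appears to go with improvement although it is unrelated to true change.

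The study aim includes finding predictors, and the introduction says that results may inform psychological support and healthcare planning. A coping scale or a health rating reported as a determinant of recovery could misdirect that.

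**Working it through.** The plan gives no figure on this point to reproduce. The check asks how often the planned regressions flag a month-3 scale X that is unrelated to change.

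**From the documents.** Three waves (section 5.3); regression-method scores (section 3.5); 1000 patients with all three waves, the upper recruitment target in section 3.6.

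**Assumed, because the documents do not give them.**
- Two-sided 0.05 per test.
- Wave-1 symptom variance set to 1, with a stable-level share of 0.5 or 0.7 and the rest independent residual at each wave.
- Slope contributing variance 0.1 by the last wave; intercept–slope covariance 0.
- Correlation ρ between X and the month-3 symptom residual, from 0 to 0.3.
- Loadings 0, 1, 3 for months 3, 6, 12. Section 3.5 has "linear models being defined as slope parameters 0, 1, 4, and 12 and quadratic slopes as 0, 1, 8 and 24", four values for three questionnaires. That is a separate inconsistency, so other sets were tried too.

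**Formula.** Symptom score y_t = I + S·λ_t + e_t. Scores are F = P Lᵀ Σ⁻¹(y − mean), with P the covariance of I and S, L the loadings and Σ the covariance of the three scores.

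**Worked case: share 0.7, slope variance 0.1/9, ρ = 0.1.**
- Slope-score weights on the 3-, 6- and 12-month scores: −0.0361, −0.0052, +0.0567. Slope-score variance: 0.00183.
- X is unrelated to true level and slope, so it covaries only with the month-3 residual: 0.1 × √0.3 = 0.0548.
- Correlation of X with the slope score: −0.0361 × 0.0548 / √0.00183 = −0.046.
- Test statistic: 0.046 × √997 ≈ 1.46. Chance of rejection: Φ(1.46 − 1.96) ≈ 0.31, where 0.05 is intended.

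**False rejection by simulation, n = 1000, both shares:**

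| ρ (assumed) | Slope score | Intercept score | 12-month score adjusted for 3-month score | 6-to-12-month change |
|---|---|---|---|---|
| 0 | about 5% | about 5% | about 5% | 3–7% |
| 0.1 | 23–31% | 12–18% | 23–34% | 3–7% |
| 0.2 | 67–82% | 33–54% | 69–88% | 3–7% |
| 0.3 | 94–99% | 60–86% | 96–100% | 3–7% |

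Across loadings 0, 1, 3; 0, 1, 4; and 1, 4, 12, the slope column widens to 17–31%, 53–84% and 86–99.5% for ρ of 0.1, 0.2 and 0.3. With 400 patients, share 0.7 and ρ = 0.3, it is 79%.

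**Second route.** Let X relate to the stable level only, at r = 0.3, and not to change (share 0.7).
- The slope-score weights sum to 0.0154, not zero, so stable level leaks into the slope score.
- The correlation is 0.3 × √0.7 × 0.0154 / √0.00183 ≈ 0.09, and the slope test rejects in about 82% of runs.
- Over r of 0.3 to 0.5 and both shares, rejection is 81–100%. The 6-to-12-month change test again stays at 3–7%.

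**Why adjustment for the 3-month score fails.** In the worked case the coefficient of X is −0.0548 × 0.7 / (1 − 0.0548²) = −0.038, or −0.037 in SDs of the 12-month score, although X predicts nothing. The 3-month score contains the same occasion residual as X, and conditioning on it creates the link.

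**The case against.** The strongest reply is that section 3.2 labels this objective exploratory, section 3.5 calls the study descriptive, and the primary outcome is untouched. Predictors of symptoms at 3 months can fairly include correlates at 3 months. This stands as a limit on severity. It does not cover section 3.5, which seeks variables that determine trajectories.

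The size of the effect is also conditional. With no shared occasion variance the error rate is nominal, and the documents do not say how large the sharing is. The false correlations are small: at ρ up to 0.3, at most about 0.14 in absolute value for slope and 0.10 for intercept. The large sample makes them significant. This stands too, although the common one-week recall of CAS-1R and HADS and the mood item in EQ-5D-5L make zero sharing hard to assume.

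A reader might infer that these scales will certainly emerge as predictors while predicting nothing. The documents do not support that. A strong link between CAS-1R and the intercept could largely reflect a real stable trait that also predicts later symptoms. The fault would lie in calling a concurrent link a determinant. Nor is the whole predictor analysis compromised: demographic, medical-record and ICU variables do not come from the questionnaire and escape the same-questionnaire problem.

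**Conclusion.** The point holds in conditional form. It is documented that CAS-1R and EQ-5D-5L share the first questionnaire with the outcome, that the predictor wave is unstated, and that EQ-5D-5L carries an anxiety/depression item. It follows that their intercept regressions cannot show prediction.

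That their slope regressions mislead depends on an assumed quantity. A shared-occasion correlation of only 0.1 raises false slope findings from about 5% to 23–31% at n = 1000, and 0.3 makes them near certain. A scale related only to stable level is flagged for slope in 81–100% of runs.

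The simulations used true rather than estimated model parameters and residuals independent between waves. If residuals persist from month 3 to month 6, the 6-to-12-month change test would lose some of its protection. The change to the plan is worth making, but the primary outcome does not depend on it.

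**What to change.** In section 3.5:
- State that the 3-month values of CAS-1R and EQ-5D-5L are the predictors, and that later waves are not used for this purpose.
- Report their relation to the intercept and to 3-month symptoms as concurrent associations. Do not interpret their slope-score regressions as determinants of change.
- Test them prospectively in two ways: against the 6- and 12-month scores, read as prediction of later level; and against the 6-to-12-month change, read as prediction of change.
- Do not rely on adjustment for the 3-month symptom score alone, because measurement error and shared occasion variance in that score bias the adjusted coefficient.
- Leave out the anxiety/depression item when EQ-5D-5L is used as a physical predictor.

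The cost is wording and a few regressions per outcome on data already collected, with no added patient burden. The change test spans 6 months rather than 9 and so has less power, which the report should acknowledge.

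### EQ-5D-5L is the only instrument listed as a physical predictor, and nothing in the plan keeps its anxiety/depression item out of the models for HADS anxiety and depression

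*Combined protocol and SAP*

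**What the plan says.** Section 3.2 of the combined protocol and SAP sets exploratory objective 1: "Identify demographic, clinical, physical and/or psychosocial predictors of depression, anxiety and/or trauma symptoms at 3-, 6- and 12-months after ICU discharge". The study summary in section 1 lists the same aim as a secondary objective.

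Section 3.3, item 1b (Physical predictors), names one instrument, EQ-5D-5L. It describes it as a "self-report measure assessing mobility, self-care, usual activities, pain/discomfort and anxiety/depression" and adds that "participants are invited to rate their health on a visual analogue scale from 0-100". It then gives the instrument its role: "In this study, EQ-5D-5L will be used as a subjective assessment of the physical function of participants".

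The other scales get a scoring rule in the same section. For HADS: "Responses are summed to produce two subscale scores". For CAS-1R: "Responses are scaled from 0%-100% and are summed to produce a total score". EQ-5D-5L gets none.

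On timing, section 5.3 says: "The following four self-report questionnaires will be administered at 3, 6 and 12 months following ICU discharge". The four are HADS, IES-6, CAS-1R and EQ-5D-5L.

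On analysis, section 3.5 says: "We will then regress predictor variables onto intercept and slope scores for all outcomes". It states no EQ-5D-5L score and no item exclusion.

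**The concern.** The objective treats physical and psychosocial predictors as separate classes. Used as written, the physical measure contains a self-report of anxiety and depression, collected in the same rounds as the HADS scores it is meant to predict. A sum or index that includes this item will tend to correlate with HADS through the shared content, whatever the role of physical function.

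What is at stake is the interpretation of the physical predictor for the two HADS outcomes. A physical association could appear when there is none. A real one could be misstated, usually upward, but slightly downward if the item relates to HADS more weakly than the physical items do. The primary prevalence estimate does not use EQ-5D-5L. IES-6 measures trauma symptoms, so its overlap with the item is only indirect.

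**Working it through.** The plan states no figure on this point, so there is none to reproduce. The text settles whether the item is excluded (it is not). The arithmetic below shows only how much that could matter.

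**Inputs.** From the documents: five domains, one of them anxiety/depression (3.3), and a target of 1000 patients answering at all three time points (3.6). Assumed, because the documents do not give them:
- an unweighted sum of items with equal variance;
- a two-sided 5% test;
- correlation among the four physical items, ρ = 0.5;
- correlation of the anxiety/depression item with HADS, r5 = 0.3, 0.5 or 0.7;
- correlation of each physical item with HADS (p) and with the anxiety/depression item (c), as stated in each case.

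**Formulas.**
- Four-domain sum with HADS: 4p / √(4 + 12ρ)
- Five-domain sum with HADS: (4p + r5) / √(5 + 12ρ + 8c)

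**Case 1, a limiting case with no physical link (p = c = 0).** The four-domain correlation is 0, so the test rejects 5% of the time. The five-domain correlation is r5 / √(5 + 6) = r5 / 3.317. Rejection is by Fisher's z.

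| r5 | correlation | rejection, N = 1000 | rejection, N = 400 (assumed) |
|---|---|---|---|
| 0.3 | 0.09 | 82% | 44% |
| 0.5 | 0.15 | 99.8% | 86% |
| 0.7 | 0.21 | >99.9% | 99% |

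Varying ρ from 0.3 to 0.7 keeps rejection at N = 1000 at 74% or above.

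**Case 1 with CAS-1R in the model.** Assume CAS-1R correlates 0.5 with HADS, 0 with the physical items, and q with the anxiety/depression item. With a = r5/√11 and b = q/√11, the partial correlation is (a − 0.5b) / √[(1 − b²)(1 − 0.25)].

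| q | r5 | partial correlation | rejection, N = 1000 |
|---|---|---|---|
| 0.3 | 0.3 / 0.5 / 0.7 | 0.052 / 0.122 / 0.192 | 38% / 97% / >99.9% |
| 0.5 | 0.3 / 0.5 / 0.7 | 0.018 / 0.088 / 0.158 | 9% / 80% / 99.9% |

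**Case 2, a real physical link (c = 0.3, no other predictors).** Here a positive finding is not false; the question is its size.

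| p | R², four domains | R², five domains, r5 = 0.3 / 0.5 / 0.7 |
|---|---|---|
| 0.3 | (1.2/√10)² = 14.4% | 16.8% / 21.6% / 26.9% |
| 0.5 | (2.0/√10)² = 40.0% | 39.5% / 46.6% / 54.4% |

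For example, with p = 0.3 and r5 = 0.7: (1.2 + 0.7)/√13.4 = 0.519, and 0.519² = 26.9%. Adding the item raises R² only if r5 exceeds 4p[√(13.4/10) − 1], which is 0.19 for p = 0.3 and 0.32 for p = 0.5.

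These figures relate an item sum to a HADS score. They were not computed for growth-model slope scores, for a weighted index or for the visual analogue scale.

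**The case against.** The strongest reply is that this is an unfinished specification and not a demonstrated circularity. A reader might infer that the team will use a five-item total or index. No section says so, and the stated purpose, physical function, could be read as limiting use to the four physical domains. The visual analogue scale does not contain the item either. This stands, and the conclusion is therefore conditional on the score used. It does not remove the point, because the instrument is assigned to the role whole.

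A reader might also infer that EQ-5D-5L is the only physical information in the study. It is not: section 5.3 collects physical co-morbidities, APACHE II and mechanical ventilation. None of these measures physical function after discharge, and none is listed under Physical predictors.

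The high rejection rates in case 1 should not be read as a forecast. They need physical items wholly unrelated to HADS, whereas the interview guide (Appendix 7) asks whether physical symptoms have affected mental well-being. They also assume a 5% test that the plan does not state, in a study it calls descriptive. They use the target of 1000, although recruitment may end in September 2022 first. A smaller N lowers the rejection rate but leaves the induced correlation unchanged. Adjusting for CAS-1R removes most of the effect in only one of the six cells shown, and the plan does not commit to joint adjustment.

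**Conclusion.** The point holds in conditional form. EQ-5D-5L is the only instrument under Physical predictors, it includes the domain that HADS measures as an outcome, and nothing excludes that item from the regressions. If a sum or index containing it is used, part of the physical association with HADS re-measures the outcome.

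Under the assumed correlations the effect can be negligible: 9% rejection against a nominal 5% with CAS-1R in the model, or R² of 40.0% becoming 39.5%. It can also be substantial: a correlation of 0.09 to 0.21 with no physical link behind it, or R² of 14% becoming 27%. The documents do not show where in this range the study would fall.

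The documents do not support inferring that the primary result is compromised, that the trauma models are affected in the same way, or that a physical association would be wholly artefact. This is a cheap improvement to one exploratory analysis and worth making.

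**What to change.** In 3.3 (1b) and 3.5, state that:
- the physical predictor uses only the pain/discomfort, mobility, self-care and usual activities domains, entered separately or as a score the team names in advance;
- the anxiety/depression item, and any sum or index containing it, is not used as a physical predictor of the HADS outcomes;
- if the visual analogue scale is used as a predictor, it is labelled overall health and not physical function.

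The overlap argument does not require a particular four-domain score, nor that the visual analogue scale be dropped as a predictor; both choices stay with the team.

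The cost is a change of text, since the item responses are already collected. The downside is that a four-domain predictor cannot be compared directly with published EQ-5D-5L index values; an index can still be reported descriptively.
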